3.5.2.1 Adverse events

Information about all adverse events including serious adverse events (SAEs), whether volunteered by the subject, discovered by investigator questioning, or detected through physical examination, laboratory test or other means, must be collected and recorded in the Adverse Event section of the study database (eCRF) irrespective of causal association. The investigator has to include information on all AEs in the individual patient eCRFs. The investigator has to commit to updating this information on a periodic basis but not later than once a month. Information on non-serious AEs is then transferred from the study database to Recordati by PPD data management on a periodic basis but not less frequently than once a month.

All AEs including SAEs occurring in association with exposure to another Recordati drug, if applicable, also have to be notified for recording in the Recordati safety database. Adverse reactions identified for non-Recordati products should be reported to the local Health Authority in accordance with national regulatory requirements for individual case safety reporting or the Marketing Authorization Holder; these will not be recorded in the Recordati safety database.

An adverse event is any undesirable sign, symptom or medical condition occurring on treatment with pasireotide s.c. even if the event is not considered to be related to pasireotide s.c. Medical conditions/diseases present before starting pasireotide s.c. treatment are only considered adverse events if they worsen after starting pasireotide s.c. Abnormal laboratory values or test results constitute adverse events only if they induce clinical signs or symptoms, are considered clinically significant or require therapy, and are recorded in the Adverse Events section. Adverse events will be collected after patients have signed the informed consent or acknowledged an equivalent document (e.g., written information) as per country regulation.

Adverse events will be assessed according to the Common Toxicity Criteria for Adverse Events (CTCAE) version 3.0. If CTCAE grading does not exist for an adverse event (document available upon request), the severity of mild, moderate, severe, and life-threatening, **or** grades 1 - 4, will be used.

In addition, all reports of the following special scenarios are also considered an adverse event irrespective if a clinical event has occurred:

- Drug-drug or drug-food interaction
- Drug use during lactation
- Lack of efficacy

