3.5.2.3 Adverse events of special interest (AESIs)

Adverse events of special interest consist of AEs for which there is a specific interest in connection with pasireotide treatment (i.e. where pasireotide may influence a common mechanism of action responsible for triggering them). The adverse events of special interest may require reporting additional information and completion of the event-specific checklists and/or questionnaires.

For pasireotide s.c. the following risks are specified as important identified risks: hypocortisolism/cortisol withdrawal syndrome, hyperglycemia, bradycardia, QTc interval prolongation, cholelithiasis, hematological abnormalities, increased liver enzymes, injection site reactions, and gastrointestinal disorders. The following risks are identified as important potential risks for pasireotide s.c.: clinically significant GH/IGF-1 decrease, hypothyroidism, pancreatitis, coagulation abnormalities, hypotension, hypocalcemia, gastrointestinal erosions/bleedings, potential interactions with cyclosporine, drugs metabolized by CYP3A4, bromocriptine, antiarrhythmic medicines and antidiabetics, off-label use in children and other indications, allergic reactions/immunogenicity, and tumor expansion. These important risks represent but are not limited to the AESIs.

Targeted follow-up may be required for the following: hypocortisolism/cortisol withdrawal syndrome, hyperglycemia, and QTc interval prolongation.

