6.5.2.1 Adverse events

The incidence of on-treatment adverse events will be summarized by system organ class and preferred term using the MedDRA dictionary. A similar table will also be produced for the post-treatment period.

Similar summary will also be provided for AESIs summarized by category and preferred term (according to the risks specified in [Section 3.5.2.3](#)).

The primary objective of this study, the number and percentage of patients having any pasireotide s.c.-related adverse event and serious adverse event will also be separately summarized by system organ class and preferred term using the MedDRA dictionary for the on-treatment period.

AE listing will be generated for the overall AEs, pasireotide s.c. related AEs, SAEs, AESIs and deaths. These listings will cover both events that occur during the on-treatment and post-treatment period however, events that occur during the post-treatment period will be flagged.

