## 3 CHANGES IN THE PLANNED ANALYSIS OF THE STUDY

Not applicable.

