#### *8.2.1.6 Absolute and percentage change from baseline in tumor size*

For time windows Month 6, 12, 18, 24, 30, and 36, absolute and percentage change from baseline in tumor volume will be summarized with descriptive statistics. Distribution-free 95% CIs will be given for the median changes. This summary will only include post-baseline evaluations for which the same method of evaluation (CT scan or MRI) as at baseline.

In addition, the absolute and percentage change from the last assessment while on pasireotide

s.c. to the last value during the 90 days after drug discontinuation will be summarized in a similar manner.

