Post-treatment AEs and post-treatment SAEs will be summarized by primary SOC, PT and maximum CTC grade in patients who discontinued pasireotide s.c. prior to completing the 3- year observation period.

In addition, (S)AEs leading to study discontinuation will be listed. Note that there is no respective flag on the eCRF. Therefore the listings will show all (S)AEs which were ongoing at the time of study discontinuation due to AE or which ended the day before.

Also summary on clinically notable AEs (patients who had grade 3/4 AEs, SAEs, AEs leading to discontinuation or other significant AEs) will be prepared for the subgroup of patients from German sites.

Specific groupings of AEs of special interest will be considered and the number of patients with at least one event in each grouping ("category") will be reported. Such groups consist of AEs for which there is a specific clinical interest in connection with pasireotide treatment (i.e. where pasireotide may influence a common mechanism of action responsible for triggering them) or AEs which are similar in nature (although not identical) within project defined group. The specific groupings of AEs as defined in the Attachment 9.2 AESI List (latest documentation available prior to database lock) will be used.

The following tables will be produced:

- AEs of special interest, regardless of relationship with pasireotide s.c., by category, preferred term and maximum CTC grade,
- SAEs of special interest, regardless of relationship with pasireotide s.c., by category, preferred term and maximum CTC grade,
- AEs of special interest, regardless of relationship with pasireotide s.c., by type (any AE, AE suspected to be related to pasireotide s.c., SAE, AE leading to discontinuation, AE requiring dose adjustment or study-drug interruption) and PT

---

Study Code: CSOM230B2410

- AEs of special interest, regardless of relationship with pasireotide s.c., by time interval of onset (0 to < 3 months, 3 to < 6 months, 6 to <9 months, etc.), category and preferred term.

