### **Occurrences of AEs and SAEs adjusted for exposure**

The exposure times by cohort is different, therefore, exposure adjusted occurrence rates will aid in the interpretation of differences in the occurrence of AEs/SAEs. Exposure adjusted occurrence rates will be presented (per 100 years of patient exposure), together with 95% confidence intervals. Summaries will be presented for treatment emergent AEs and SAEs.

Confidence intervals will be derived assuming a Poisson process for the occurrence of AEs (SAEs). See Section 5.4 for further details.

Summaries of exposure adjusted occurrence rates will be produced for AEs and SAEs by PT. Only AEs (SAEs) with more than 2 occurrences per preferred term will be displayed.

The analyses on occurrences of AEs and SAEs will be repeated by country.

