## 9.2 AESI LIST

Category	Adverse Event Term
AESI Bradycardia related AEs	Atrial conduction time prolongation (PT) Atrioventricular block (PT) Atrioventricular block complete (PT) Atrioventricular block second degree (PT) Atrioventricular dissociation (PT) Bradycardia (PT) Central bradycardia (PT) Conduction disorder (PT) Defect conduction intraventricular (PT) Electrocardiogram PQ interval prolonged (PT) Electrocardiogram PR prolongation (PT) Electrocardiogram QRS complex prolonged (PT) Electrocardiogram QT prolonged (PT) Long QT syndrome (PT) Paroxysmal atrioventricular block (PT) Sinoatrial block (PT) Sinus bradycardia (PT)
AESI Coagulation related AEs	Blood fibrinogen decreased (PT) Blood thrombin decreased (PT) Blood thromboplastin abnormal (PT) Blood thromboplastin decreased (PT) Coagulation factor IX level decreased (PT) Coagulation factor V level decreased (PT) Coagulation factor VII level decreased (PT) Coagulation factor X level decreased (PT) Coagulation factor decreased (PT) Hypofibrinogenaemia (PT) International normalised ratio abnormal (PT) Prothrombin level decreased (PT) Prothrombin time prolonged (PT) Prothrombin time ratio decreased (PT) Thrombin time prolonged (PT)
AESI Gallbladder and biliary related AEs	Bile duct necrosis (PT) Bile duct obstruction (PT) Bile duct stenosis (PT) Bile duct stone (PT) Bile output abnormal (PT) Bile output decreased (PT)

Study Code: CSOM230B2410

Category	Adverse Event Term
	Bile output increased (PT)
	Biliary cirrhosis (PT)
	Biliary colic (PT)
	Biliary dilatation (PT)
	Biliary dyskinesia (PT)
	Biliary dyspepsia (PT)
	Biliary fibrosis (PT)
	Biliary fistula (PT)
	Biliary ischaemia (PT)
	Biliary tract disorder (PT)
	Bilirubin conjugated abnormal (PT)
	Bilirubin conjugated increased (PT)
	Bilirubin excretion disorder (PT)
	Bilirubin urine present (PT)
	Bilirubinuria (PT)
	Blood alkaline phosphatase abnormal (PT)
	Blood alkaline phosphatase increased (PT)
	Blood bilirubin abnormal (PT)
	Blood bilirubin increased (PT)
	Blood bilirubin unconjugated increased (PT)
	Cholangiogram abnormal (PT)
	Cholecystectomy (PT)
	Cholecystitis (PT)
	Cholecystitis acute (PT)
	Cholecystitis chronic (PT)
	Cholecystogram intravenous abnormal (PT)
	Cholecystogram oral abnormal (PT)
	Cholelithiasis (PT)
	Cholelithiasis migration (PT)
	Cholelithiasis obstructive (PT)
	Cholestasis (PT)
	Deficiency of bile secretion (PT)
	Endoscopy biliary tract abnormal (PT)
	Gallbladder disorder (PT)
	Gallbladder enlargement (PT)

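### Tumor expansion is a named important potential risk, but the SAP's AESI list has no category for it, so the planned AESI tables would omit it

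*SAP*

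**What the plan says.** **The risk.** Protocol 3.5.2.3 sets out nine important identified and eleven important potential risks. The potential risks end with "off-label use in children and other indications, allergic reactions/immunogenicity, and tumor expansion".

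**The commitment.** Protocol 6.5.2.1, after describing the general AE tables, states: "Similar summary will also be provided for AESIs summarized by category and preferred term (according to the risks specified in". What follows is a cross-reference to the risk list just described.

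**The implementation.** SAP 8.4.1 states: "The specific groupings of AEs as defined in the Attachment 9.2 AESI List (latest documentation available prior to database lock) will be used". Attachment 9.2 runs from "AESI Bradycardia related AEs" to the QT-prolongation group. SAP section 3, on changes to the planned analysis, reads "Not applicable".

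**When growth counts as an AE.** Protocol 3.5.2.1: "Abnormal laboratory values or test results constitute adverse events only if they induce clinical signs or symptoms, are considered clinically significant or require therapy".

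**Measured tumor size.** This is a secondary efficacy endpoint (Protocol 2.2.1 and 6.5.1). For Months 6 to 36, SAP 8.2.1.6 plans this: "absolute and percentage change from baseline in tumor volume will be summarized with descriptive statistics. Distribution-free 95% CIs will be given for the median changes". It is limited to scans by the same method as at baseline. SAP 8.2.1 adds a repeated-measures model.

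**The concern.** This is a post-authorization safety study. The AESI tables are where a reader will look for each risk the protocol singles out. If a named risk has no category, its absence from those tables can be misread as absence of events. Tumor-growth AEs would have to be identified by preferred term in the general tables.

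Growth seen on a scan but not judged clinically significant need not be an AE. It would be visible only through window-level means, medians and extremes.

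**Working it through.** The plan gives no figure to reproduce. The sample size is not statistically based and no hypothesis is tested. The check sets the two risk lists side by side and then follows the imaging windows.

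**1. Risks against categories**

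- Protocol 3.5.2.3: 9 identified + 11 potential = 20 risks. Removing drug interactions and off-label use, which are not event types, leaves 18.
- Attachment 9.2 has 13 categories: bradycardia, coagulation, gallbladder/biliary, growth hormone deficiency, hyperglycemia, hypocortisolism, hypotension, hypothyroidism, injection site, liver, low blood cell, pancreatitis and QT prolongation. Each matches one of the 18.
- Unmatched: 18 − 13 = 5, and 5/18 = 27.8%.

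| Risk without a category | Where it would still be seen |
|---|---|
| Tumor expansion | General SOC/PT tables and listings, if reported as an AE |
| Hypocalcemia | Same |
| Gastrointestinal erosions/bleedings | Same |
| Allergic reactions/immunogenicity | Partly in the injection-site category (hypersensitivity, rash, pruritus, urticaria); otherwise general tables |
| Gastrointestinal disorders | As a system organ class row in every SOC table |

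No preferred term for tumor growth appears under any of the 13 headings.

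**2. Effect on the AESI tables**

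SAP 8.4.1 plans four: AESIs by grade, serious AESIs by grade, AESIs by type, and AESIs by time of onset. All draw on Attachment 9.2, so as printed a tumor-growth AE enters 0 of 4.

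**3. Measured tumor size**

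- The first post-baseline window in SAP Table 6-3 opens on Day 137. On-treatment scans on Days 2 to 136 (136 − 2 + 1 = 135 days) fall in no Month window.
- Exception: under Table 6-1, a cohort 2 patient with no earlier scan may use one taken up to 6 months after first dose as baseline.
- Efficacy values count as on-treatment up to 3 days after last dose. Last dose on Day 133 gives 133 + 3 = 136, before the first window. Last dose on Day 134 gives 137, the first usable day. In months, 133/30.4375 = 4.4.
- So a patient whose last dose is on or before Day 133, or who otherwise has no same-method on-treatment scan on or after Day 137, contributes no observed change from baseline to SAP 8.2.1.6.
- Scans 4 to 90 days after last dose are compared only with the last on-treatment scan, not with baseline.

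**4. What a median can leave unseen (illustration only)**

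The upper limit of the distribution-free 95% CI for a median is the ordered value of rank n − k + 1, where k is the largest rank with P(Bin(n, 0.5) ≤ k − 1) ≤ 0.025. If that limit is below zero, up to k − 1 patients can still have a growing tumor.

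| n with paired scans (assumed) | Ranks of limits | Growing tumors possible |
|---|---|---|
| 30 | 10, 21 | 9 (30%) |
| 50 | 18, 33 | 17 (34%) |
| 100 | 40, 61 | 39 (39%) |
| 200 | 86, 115 | 85 (42.5%) |

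This is a property of the summary, not a forecast. The documents give no expected growth rate.

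**The case against.** **The list can still change.** SAP 8.4.1 uses the latest version of the list before lock, so the omission is conditional. That is right, and it makes the repair easy. It does not supply the category.

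**Section 3 may not be contradicted.** SAP 4.1 ties the analysis to protocol Section 6 as amended in September 2013, and the AESI list was updated in July 2016. Whether the 2013 list named tumor expansion cannot be seen. An outdated reference is a plausible explanation, but the SAP was revised in September 2023 and should match the current protocol.

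**Tumor-growth AEs are not lost.** A reader might infer that they would go unreported. The documents do not support this. Such AEs enter the general SOC/PT tables and, where applicable, the related, serious and discontinuation summaries and listings. The display rule "Only AEs (SAEs) with more than 2 occurrences per preferred term will be displayed" applies only to the exposure-adjusted tables and to every term alike. How many tumor events it would hide depends on how many preferred terms they are coded to, which is unknown.

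**Early stoppers are not all excluded.** A reader might infer that patients who stop early never enter a tumor summary, perhaps because they stopped for growth. A patient with a same-method on-treatment scan inside a Month window does enter, and an end-of-treatment scan can serve. Nothing links stopping to growth. Protocol Table 3-1 suggests imaging at baseline, every 12 months, and at end of treatment and of study, so few on-treatment scans before Day 137 may exist. Those that do can still serve as the last on-treatment value for the 90-day comparison.

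**The imaging plan follows the protocol.** Tumor size is an efficacy endpoint there, is absent from the Protocol 6.5.2 safety list, and will have a minimum and maximum change reported per window. This stands, so a patient-level display is an improvement, not a correction. The maximum, however, is one unidentified value per window and does not say how many tumors grew.

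**Conclusion.** The mismatch between Protocol 3.5.2.3/6.5.2.1 and SAP Attachment 9.2 is real and should be resolved before lock. Its size is one named risk absent from all four AESI tables. Hypocalcemia, gastrointestinal erosions/bleedings and allergic reactions beyond injection-site terms also lack a category, and gastrointestinal disorders are covered only as a SOC row. Reading the 5 of 18 as five unreported risks would go too far.

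The conclusion assumes that Attachment 9.2 ends where it is printed and is applied in that form. The headings are alphabetical, so a tumor heading would fall after the last one. The gastrointestinal and hypocalcemia headings would fall inside the printed range and are missing too, so a lost final page would not explain the whole gap.

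On imaging, the supportable statement is narrow: no planned output counts or lists patients whose tumors grew, and certain scans are never compared with baseline. No effect on results can be estimated from the documents.

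**What to change.** **Before database lock**

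1. Add a tumor-expansion category, with its MedDRA preferred terms, to Attachment 9.2.
2. For hypocalcemia, gastrointestinal erosions/bleedings, allergic reactions/immunogenicity and gastrointestinal disorders, either add a category or state in SAP section 3 why there is none.

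The cost is SAP wording and one to five list categories, using AE data already collected. SAP 8.4.1 already allows the list to be updated.

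**Optional, low cost**

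3. Keep SAP 8.2.1.6 as the efficacy summary and add one per-patient listing of tumor-volume change from baseline, same imaging method. Use all post-baseline on-treatment scans, including Days 2 to 136. Flag scans 4 to 90 days after last dose separately, so that on-drug and off-drug change are not mixed. Show the number of scans per patient.

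The listing uses imaging data already collected. Scans are read locally, and a patient's largest reading is biased upward by measurement error. For three independent normal readings with no true change, the expected maximum is 3/(2√π) = 0.85 SD. That is why the scan count must be shown.

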#### *8.2.1.7 Absolute and percentage change from baseline in patient-reported outcomes (Cushing QoL and EURO QoL)*

##### **Cushing QoL Questionnaire**

Completion of nine or more items of the 12-item CushingQoL questionnaire is required for it to be considered evaluable for that assessment. A higher score is indicative of better patient quality of life. The best possible standardized score is 100, and the worst possible standardized score is 0.

The standardized score for the CushingQoL and its absolute and percentage change from baseline will be summarized with descriptive statistics for time windows Month 6, 12, 18, 24, 30, and 36. Distribution-free 95% CIs will be given for the median changes.

The calculation of the standardized score is described in Appendix 16.1.9, Section 4.3.1.1.

### EQ-5D-3L Questionnaire

Responses to the EQ-5D will be summarized into a single index, in accordance with the user manual for EQ-5D-3L. The higher the index the better the patient's health state.

The EQ-5D visual analogue scale (VAS) records the respondent's self-rated health on a 20 cm vertical, visual analogue scale with endpoints labeled 'the best health you can imagine' and 'the worst health you can imagine'. This information can be used as a quantitative measure of health as judged by the individual respondent.

For time windows Month 6, 12, 18, 24, 30, and 36:

- the index for EQ-5D questionnaire and its absolute change from baseline will be summarized with descriptive statistics. Distribution-free 95% CIs will be given for the median changes.
- the result from the EQ VAS scale and its absolute and percentage change from baseline will be summarized with descriptive statistics. Distribution-free 95% CIs will be given for the median changes.

[figure not shown]
The calculation of the index is described in Appendix 16.1.9, Section 4.3.1.1.

### 8.3 EXTENT OF EXPOSURE

All study medication data will be summarized using the safety set.

Duration of exposure will be summarized by appropriate descriptive statistics for each cohort.

**Figure 8-1 Treatment start and duration of exposure in Cohorts 1 and 2**

The following definitions will be used:

**Treatment start date for cohort 1:** defined as the first date at which a non-zero dose of pasireotide s.c. was administered during the study and recorded on the DAR (e)CRF.

**Treatment start date for cohort 2:** defined as the first date at which a non-zero dose of pasireotide s.c. was administered prior to study entry and recorded on the CMD (e)CRF.

**Treatment end date (same for the 2 cohorts):** defined as the last date at which a non-zero dose of study drug was administered and recorded on the DAR (e)CRF. If the end date of the last dosing period with a non-zero dose is missing, the "last known date patient took study drug" (as reported on the completion panel) will be used.

**Duration of exposure** will be calculated for each cohort separately as the number of days from the treatment start date to the treatment end date, which are defined for the two cohorts above, including days with interruptions.

$$\text{duration of exposure} = \text{treatment end date} - \text{treatment start date} + 1$$

The derivation of treatment start and end date is described in Appendix 16.1.9 of the CSR, Section 4.2.1.

**Duration of on-study exposure** will be calculated as the number of days from the date of first dose after informed consent (IFC) to the treatment end date, including days with interruptions.

$$\text{duration of on study exposure} = \text{treatment end date} - \text{date of first dose after IFC} + 1$$

The derivation of treatment start and end date is described in Appendix 16.1.9 of the CSR, Section 4.2.1.

**Actual mean daily dose or actual dose intensity** of pasireotide s.c. will be calculated for each patient as total cumulative dose at the time of last administration divided by the duration of exposure.

Duration of exposure, duration of on-study exposure and actual dose intensity while in the study will be summarized with descriptive statistics by cohorts. In addition, a frequency table will show the number and percentage of patients per duration of exposure category (<=1 month, >1 to 3 months, >3 to 6 months, >6 to 12 months, >12 to 24 months, >24 to 36 months,

>36 months). This summary will be prepared for the safety set and the subgroup of patients from German sites.

The number and percentage of patients who used pasireotide as single therapy, who used it as combination therapy, and who switched from single to combination therapy (or vice versa) will be presented by time period (Day 1 to Day 30, Day 1 to Day 91, Day 1 to 183, etc). Each summary of a time period will only include patients who still received pasireotide s.c. at the end of the time period. Patients will be split up into the three groups based on the following definitions:

- Patients are considered to be on single therapy throughout a period if they did not receive any other medication than pasireotide for Cushing's disease during this period.
- Patients are considered to be on combination therapy throughout a period if they received pasireotide in combination with other medications for Cushing's disease throughout this period. Interruptions of less than 10 days are not considered a switch to single therapy.

---

Study Code: CSOM230B2410

- Patients who switched from single to combination therapy or vice versa are patients who do not fulfill the condition for single therapy and combination therapy throughout the period, as outlined above.
- The frequency of dose changes will be classified as 'no change', 1, 2, 3, >3 changes. Similar classifications will be done for dose increases and dose reductions (including interruptions). The frequencies will be summarized by time window (see Table 6-2 in Section 6.1.7), overall and by reason.

